7.6.7. Shifts from baseline in Mean overall PTA Categories

• Computation of the Endpoint

Mean overall PTA for each ear will be categorized into <26, 26-40, 41-55, 56-70, and >70 for each visit and shifts from baseline to each post-baseline visit will be computed (e.g., 26-40 to 41-55).

• Analysis of the Endpoint

The distribution in the shift in mean overall PTA categories for treated ears from baseline to each post-baseline visit will be summarized using frequencies and percentages by visit and treatment group for subjects in the FAS.

7.6.8. Mean low AC dB HL threshold (AC over 0.25, 0.5, 1, and 2 kHz)

• Computation of the Endpoint

At each visit and by ear (left, right), the mean low AC dB HL threshold will be derived by averaging the AC audiometry dB HL thresholds over 0.25, 0.5, 1, and 2 kHz frequencies. Left and right ears will be mapped to treated and untreated for analysis. Missing values will be imputed per Section 7.6.

• Analysis of the Endpoint

The mean low AC dB HL threshold will be summarized descriptively for treated ears by visit and treatment group for subjects in the FAS.

7.6.9. Mean high AC dB HL threshold (AC over 3, 4, 6 and 8 kHz)

• Computation of the Endpoint

At each visit and by ear (left, right), the mean high AC dB HL threshold will be derived by averaging the AC audiometry dB HL thresholds over 3, 4, 6 and 8 kHz frequencies. Left and right ears will be mapped to treated and untreated for analysis. Missing values will be imputed per Section 7.6.

• Analysis of the Endpoint

The mean high AC dB HL threshold will be summarized descriptively for treated ears by visit and treatment group for subjects in the FAS.

7.6.10. Air-Bone Imbalance at 0.5, 1, 2, 3, and 4 kHz

• Computation of the Endpoint

At each visit and by ear (left, right), Air-Bone imbalance is computed as AC-BC dB HL thresholds at 0.5, 1, 2, 3, and 4 kHz. Left and right ears will be mapped to treated and untreated for analysis. Missing threshold values will be imputed per Section 7.6 prior to the derivation.

• Analysis of the Endpoint

The Air-Bone imbalance at each frequency (0.5, 1, 2, 3, and 4 kHz) will be summarized descriptively for treated ears by visit and treatment group for subjects in the FAS.

7.6.11. Shift from baseline in Air-Bone Imbalance at 0.5, 1, 2, 3, and 4 kHz

• Computation of the Endpoint

Air-bone imbalance at each frequency will be categorized into ≤10 dB HL versus >10 dB HL for each visit and shifts from baseline to each post-baseline visit will be computed (e.g., ≤10 dB HL to >10 dB HL).

• Analysis of the Endpoint

The distribution in the shift in air-bone imbalance for treated ears at each frequency from baseline to each post-baseline visit will be summarized using frequencies and percentages by visit and treatment group for subjects in the FAS.

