#### **10.5.2 Inclusion Criteria**

To be eligible for study entry subjects must satisfy all the following criteria:

1. Subject has read and voluntarily signed the Informed Consent Form (ICF) after all questions have been answered and prior to any study-mandated procedure.
2. Adult aged 18-65 years inclusive at Screening.
3. Documented medical history consistent with acquired, adult onset, sensorineural hearing loss associated with noise-induced SNHL (NIHL) or idiopathic sudden SNHL (SSNHL) (documented audiogram at least 6 months prior to screening required).
4. A pure tone average at the Screening Visit of 35-85 dB at 500Hz, 1000Hz, 2000Hz, and 4000Hz in the ear to be injected.
5. Ability to communicate well with the Investigator and is willing to comply with and complete all the study procedures.

6. Female subjects must be of non-childbearing potential or will need to utilize two methods of highly effective contraception during the study participation (e.g. hormonal contraception and condom or an intrauterine device and condom) or remain abstinent. Male subjects should use condoms with spermicide during the course of the study or remain abstinent. Subjects should not donate sperm or ova during the study period.
7. Have met additional masked criteria as determined by EDC.

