### **10.5.3 Exclusion Criteria**

Subjects will be excluded from the study if one or more of the following criteria are applicable:

1. Subject has previously been randomized in a FX-322 clinical trial.
2. Perforation of tympanic membrane or other tympanic membrane disorders that would interfere with the delivery and safety assessment of an intratympanic medication or reasonably be suspected to affect tympanic membrane healing after injection in study ear. This includes a current tympanostomy tube.
3. Any conductive hearing loss of greater than 15 dB at a single frequency or greater than 10dB at two or more contiguous octave frequencies in the study ear at the Screening visit.
4. Active chronic middle ear disease or a history of major middle ear surgery, as an adult, in the ear to be injected.
5. Subject has had an intratympanic injection in either ear within 3 months of the screening visit.
6. Evidence of or previous diagnosis of auditory neuropathy, traumatic brain injury, “central” hearing loss, or genetic hearing loss.
7. History of chronic, recurrent clinically significant vestibular symptoms.
8. History of Bilateral Sudden Sensorineural Hearing Loss or Recurrent Sudden Sensorineural Hearing Loss.
9. History of clinically significant systemic autoimmune disease (e.g. rheumatoid arthritis, Sjogren’s syndrome, multiple sclerosis, psoriasis).
10. History of head or neck radiation, treatment, or exposure to platinum based chemotherapy drugs or aminoglycosides.
11. Exposure to another investigational drug within 28 days prior to screening visit.
12. Evidence of any active or chronic disease or condition that could interfere with, or for which the treatment of might interfere with, the conduct of the study, or that would pose an unacceptable risk to the subject in the opinion of the investigator following a detailed medical history, physical examination, and vital signs (systolic and diastolic blood pressure, pulse rate, body temperature).
13. Positive urine pregnancy test or breast-feeding.
14. Any known factor, condition, or disease that, in the view of the Investigator, might interfere with treatment compliance, study conduct or interpretation of the results.

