7.6. Pure Tone Audiometry

Standard Pure Tone Audiometry will be measured to determine a subject's threshold for hearing at various frequencies and will be performed at the Screening/Start of Lead-In, Lead-In, End of Lead-In/Treatment, Day 30, Day 60, Day 90, Day 180, and Day 270 visits. This will be performed on a calibrated audiometer by a licensed audiologist. The following frequencies will be obtained: Air: 0.25, 0.5, 1, 2, 3, 4, 6, and 8 kHz; Bone: 0.5, 1, 2, 3, and 4 kHz. If both masked and unmasked results are available for the same visit, date, ear, and frequency, the masked results will be used for analysis. Post-Screening PTA thresholds with missing response values, specifically, no response due to a subject's audiometric threshold greater than the maximum calibrated dB of the equipment at a given frequency, will be imputed using the maximum dB for the audiometry equipment plus 5 dB. The value, maximum dB for the audiometry equipment plus 5 dB, was collected on the CRF as audiometer upper limit and the result will be classified as no signal at that frequency. Missing response values at Screening will not be imputed and remain missing.

Pure tone audiometry results will be presented in a data listing for the FAS.

- 7.6.1. Air and Bone Conduction audiometry dB HL thresholds by frequency
 - Computation of the Endpoint

At each visit and by ear (left, right), the AC and BC audiometry dB HL thresholds will be recorded for each frequency (Air: 0.25, 0.5, 1, 2, 3, 4, 6, and 8 kHz; Bone: 0.5, 1, 2, 3, and 4 kHz). Left and right ears will be mapped to treated and untreated for analysis. Missing values will be imputed per Section 7.6.

• Analysis of the Endpoint

Separately for AC and BC, the hearing threshold at each frequency will be summarized descriptively for treated and untreated ears separately by visit and treatment group for subjects in the FAS.

A line plot of the mean AC audiometry thresholds by frequency will be prepared for treated and untreated ears for each treatment group with lines connecting each point.

7.6.2. Mean overall PTA (AC over 0.5, 1, 2, and 4 kHz) and BCA (BC over 0.5, 1, 2 and 4 kHz)

• Computation of the Endpoint

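### Where bone conduction gives no response, the air-bone imbalance in SAP 7.6.10 and 7.6.11 is not measurable, and the imputed value can be tabulated as a gap above 10 dB if the bone-conduction limit is far enough below the air-conduction limit

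*SAP*

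**What the plan says.** SAP 7.6.10 gives the derivation: "Air-Bone imbalance is computed as AC-BC dB HL thresholds at 0.5, 1, 2, 3, and 4 kHz". It then adds that "Missing threshold values will be imputed per Section 7.6 prior to the derivation".

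SAP 7.6 defines the case that is imputed, "no response due to a subject's audiometric threshold greater than the maximum calibrated dB of the equipment at a given frequency", and the value: such thresholds "will be imputed using the maximum dB for the audiometry equipment plus 5 dB". The imputed value "was collected on the CRF as audiometer upper limit and the result will be classified as no signal at that frequency". The rule covers both AC and BC from the Lead-In visit onwards; Screening values are not imputed. No numeric limit is given, and the text does not say whether the CRF holds separate limits for AC and BC.

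SAP 7.6.11 continues: "Air-bone imbalance at each frequency will be categorized into" at most 10 dB HL versus more than 10 dB HL, with shifts tabulated from baseline to each later visit. Neither 7.6.10 nor 7.6.11 uses the no-signal classification. Both are descriptive summaries in treated ears of the FAS.

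On eligibility, protocol 10.5.2 requires "A pure tone average at the Screening Visit of 35-85 dB" over 0.5, 1, 2 and 4 kHz in the ear to be injected. Protocol 10.5.3 excludes "Any conductive hearing loss of greater than 15 dB at a single frequency" in the study ear at Screening, or more than 10 dB at two or more contiguous octave frequencies.

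**The concern.** A no-response threshold is right-censored: it lies somewhere above what the equipment can deliver. Subtracting a stand-in for a censored BC value from an AC value does not estimate the air-bone gap. If BC runs out of range before AC does, part of an ordinary sensorineural threshold is carried into the difference and looks like a conductive component.

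Protocol 8.2 names both conductive and sensorineural hearing loss among the risks of intratympanic injection. The air-bone shift table is the SAP summary that tries to tell the two apart from thresholds within an ear. At affected frequencies it could show a gap at baseline that the ear does not have. It could also record worsening of AC, with no conductive change, as a shift to more than 10 dB.

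**Working it through.** The SAP states no figure for air-bone imbalance, so there is nothing to reproduce. The check applies its rule to a constructed ear.

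**Inputs from the documents.** Gap = AC − BC (7.6.10); no response is recorded as limit + 5 dB (7.6); cut-off 10 dB (7.6.11); four-frequency average of 35 to 85 dB at entry (protocol 10.5.2).

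**Assumptions.** The ear is purely sensorineural, with true AC = true BC = T and a true gap of 0. Thresholds move in 5 dB steps. The BC limit L and the AC limit A are not in the documents; L is taken as 60, 70, 80 or 100 dB and A as 110 or 120 dB, plus the case L = A.

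**1. BC no response, AC measured (L < T ≤ A).** Reported gap = T − (L + 5). It exceeds 10 dB when T > L + 15.

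| Assumed L | Last T reported as ≤10 dB | First T reported as >10 dB |
|---|---|---|
| 60 | 75: 75 − 65 = 10 | 80: 80 − 65 = 15 |
| 70 | 85: 85 − 75 = 10 | 90: 90 − 75 = 15 |
| 80 | 95: 95 − 85 = 10 | 100: 100 − 85 = 15 |

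**2. Both no response.** Reported gap = (A + 5) − (L + 5) = A − L, whatever the ear. Examples: 110 − 70 = 40 dB; 110 − 80 = 30 dB; 110 − 100 = 10 dB, which stays in the lower category.

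**3. Equal limits (L = A).** The reported gap is 0 at every T, so no false gap arises. When neither responds, that 0 still comes from the equipment and not from the ear.

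**4. Shifts, with L = 70.**
- BC no response at both visits, AC from 85 to 90: 85 − 75 = 10, then 90 − 75 = 15. This is tabulated as a shift from ≤10 to >10 dB. The reverse change gives the reverse shift.
- True AC and BC both worsening from 70 to 90: 70 − 70 = 0, then 90 − 75 = 15. A purely sensorineural change is tabulated as a new gap.
- AC unchanged and BC no response at both visits: the same value twice, so no shift.

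**5. Can such thresholds enter the trial?** Yes. Thresholds of 55, 75, 100 and 110 dB average 340/4 = 85 dB. An ear need not be at the ceiling: 40, 60, 85 and 95 dB average 280/4 = 70 dB, and with L = 70 the 95 dB frequency reports 95 − 75 = 20 dB.

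**6. The opposite case: AC no response, BC measured.** With A = 110 and BC = 70, the reported gap is 115 − 70 = 45 dB, and the true gap exceeds 110 − 70 = 40 dB. Here the imputed value marks a real gap and works as a lower bound.

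**The case against.** A reader might infer that severe sensorineural ears as a group will be reported with conductive gaps they do not have. The documents do not support that. It needs a BC limit well below the AC limit, and the SAP mentions only an audiometer upper limit on the CRF. With equal limits the false gap is zero, and with limits of 110 and 100 dB it never exceeds 10 dB. Only frequencies without a BC response are affected, and nothing in the documents shows how many there will be. This objection stands, and the point is conditional because of it.

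Nor is every baseline gap above 10 dB an artefact. The exclusion allows an isolated gap of up to 15 dB at one frequency, and it applies at Screening only. That stands too.

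The table is not the only place where conductive change would appear. The SAP has shift tables for otoscopy (8.6.3) and tympanometry (8.6.4), AC and BC thresholds by frequency (7.6.1), and the adverse events of special interest defined in the protocol. The imputation rule is the same in both arms, and the single 5 dB shift occurs only at the category boundary. All this limits the consequence. It does not make the computed value meaningful where BC is censored.

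Finally, restricting the derivation to frequencies with both AC and BC measured would discard step 6, where the imputed value points to a genuine gap. That is right, and a narrower fix is needed.

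**Conclusion.** The point holds as a conditional one. Wherever BC is no response, 7.6.10 reports a number for a gap that was not measured. If neither conduction route responds, that number is the difference between two equipment limits and says nothing about the ear, whatever the limits are. If only BC fails to respond, a purely sensorineural frequency is placed above 10 dB once AC exceeds the BC limit by more than 15 dB, and AC worsening alone can then appear as a shift. How often this happens depends on equipment limits and threshold distributions that the documents do not give, and it may be rare or absent.

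The effect is confined to the descriptive tables of 7.6.10 and 7.6.11. Neither feeds the fixed testing sequence in SAP 7.1.4, so no primary or key secondary result changes. The change is still worth making: the tables bear on a named risk of the injection, and the flag it needs is already defined in 7.6.

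**What to change.** In SAP 7.6.10 and 7.6.11:

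- Do not compute the imbalance at any frequency where BC is classified as no signal, alone or together with AC. Show these ears in a separate row of the summary and shift tables, labelled *not measurable (BC no response)*.
- Where AC is no signal and BC is measured, keep the imputed value for the two-way category, flagged as a lower bound, and leave it out of the means. The flag matters because a lower bound of 10 dB or less does not show that the true gap is that small.
- State whether the upper limit on the CRF is recorded separately for AC and BC.

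Leave the imputation in 7.6 unchanged for all other endpoints.

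The cost is a few sentences and one table row. SAP 7.7.6 to 7.7.8 already tabulate no-signal status for the extended high frequencies, so the approach is not new to this plan. The downside is that fewer ears contribute at the worst frequencies. If the AC and BC limits turn out to be equal, the change only moves unmeasured values out of the numerical summaries.

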7.7. Extended High Frequency Audiometry

Extended high frequency audiometry will be performed to determine a subject's threshold for hearing at frequencies beyond those in standard pure tone audiometry at the Screening/Start of Lead-In, Lead-In, End of Lead-In/Treatment, Day 30, Day 60, Day 90, Day 180, and Day 270 visits. This will be performed on a calibrated audiometer by a licensed audiologist. The following frequencies will be obtained: Air: 9, 10, 11.2, 12.4, 14, and 16 kHz. Because some audiometers use center frequencies that vary by small amounts, sites should use the threshold at the closest listed center frequency (e.g., 11 kHz may be used for 11.2 kHz; 12.5 kHz may be used for 12.4 kHz). If both masked and unmasked results are available for the same visit, date, ear, and frequency, the masked results will be used for analysis.

Post-Screening PTA thresholds with missing response values, specifically, no response due to a subject's audiometric threshold greater than the maximum calibrated dB of the equipment at a given frequency, will be imputed using the maximum dB for the audiometry equipment plus 5 dB. The value, maximum dB for the audiometry equipment plus 5 dB. The value, maximum dB for the result will be classified as no signal at that frequency. Missing response values at Screening will not be imputed and remain missing.

Extended high frequency audiometry results will be presented in a data listing for subjects in the FAS.

7.7.1. Air audiometry dB HL thresholds by frequency

• Computation of the Endpoint

At each visit and by ear (left, right), the AC audiometry dB HL thresholds will be recorded for each frequency (9, 10, 11.2, 12.4, 14, and 16 kHz). Left and right ears will be mapped to treated and untreated for analysis. Missing values will be imputed per Section 7.7.

• Analysis of the Endpoint

Descriptive summaries and the line plot will be performed for AC audiometry dB HL thresholds as described in Section 7.6.1.

7.7.2. Mean dB HL threshold (AC over 9-16 kHz)

• Computation of the Endpoint

At each visit and by ear (left, right), the mean dB HL threshold will be derived by averaging the AC audiometry dB HL thresholds over 9-16 kHz frequencies. Left and right ears will be mapped to treated and untreated for analysis. Missing values will be imputed per Section 7.7.

• Analysis of the Endpoint

The mean dB HL threshold will be summarized descriptively for treated ears by visit and treatment group for subjects in the FAS.

7.7.3. AC improvement ≥10 dB HL and ≥15 dB HL from baseline, separately, for two contiguous frequencies

• Computation of the Endpoint

AC improvement ≥10 dB HL from baseline for two contiguous frequencies at each postbaseline visit for treated ears will be computed as 1 if the post-baseline threshold – baseline threshold is ≥10 dB HL for two contiguous frequencies and as 0, otherwise. The endpoint will utilize imputed values per Section 7.7. The AC improvement ≥15 dB HL will be derived using the same approach.

• Analysis of the Endpoint

AC improvement ≥10 dB HL from baseline for two contiguous frequencies will be summarized using frequencies and percentages for treated ears by visit and treatment group for subjects in the FAS. The summary will be repeated for AC improvement ≥15 dB HL.

7.7.4. AC improvement ≥15 and ≥20 dB HL from baseline, separately, for any frequency

• Computation of the Endpoint

AC improvement \geq 15 dB HL from baseline for any frequency at each post-baseline visit for treated ears will be computed as 1 if the post-baseline threshold – baseline threshold is \geq 15 dB HL for any frequency and as 0, otherwise. The endpoint will utilize imputed values per Section 7.7. The AC improvement \geq 20 dB HL will be derived using the same approach.

• Analysis of the Endpoint

AC improvement ≥15 dB HL from baseline for any frequency will be summarized using frequencies and percentages for treated ears by visit and treatment group for subjects in the FAS. The summary will be repeated for AC improvement ≥20 dB HL.

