7.7.5. AC composite improvement from baseline

• Computation of the Endpoint

The first AC composite improvement endpoint is defined as the occurrence of either or both of the following conditions for a given subject's ear for a given visit: 1) AC improvement ≥ 10 dB HL from baseline for two contiguous frequencies as described in Section 7.7.3 or 2) AC improvement ≥ 15 dB HL from baseline for any frequency as defined in Section 7.7.4.

The second AC composite improvement endpoint is defined as the occurrence of either or both of the following conditions for a given subject's ear for a given visit: 1) AC improvement \geq 15 dB HL from baseline for two contiguous frequencies as described in Section 7.7.3 or 2) AC improvement \geq 20 dB HL from baseline for any frequency as defined in Section 7.7.4.

• Analysis of the Endpoint

The incidence of each AC composite improvement endpoint at each post-baseline visit for treated ears will be summarized using frequencies and percentages for treated ears by visit and treatment group for subjects in the FAS.

In treated ears only for subjects in the FAS, post-baseline treatment group comparisons through day 90 for incidence of AC composite improvement from baseline may be analyzed using a GEE model. With the binomial distribution assumption and logit link, the model will include fixed effects of treatment group, visit, interaction between visit and treatment group, baseline mean dB HL threshold (AC over 9-16 kHz), interaction between baseline mean dB HL threshold (AC over 9-16 kHz) and visit, and randomization stratification factors. If the model fails to converge, the randomization stratification factors will be excluded from the model. The odds ratios along with 95% CIs and p-values between treatment groups will be reported by post-baseline visit.

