7.7.6. Shift from baseline of no signal to any signal by frequency

• Computation of the Endpoint

For each frequency, shifts from no signal to any signal will be computed in subjects in the FAS with no signal (missing/imputed hearing response) at baseline in the treated ear. At each post-baseline visit, subjects with any signal (any non-missing/not imputed hearing response) in the treated ear will be flagged as 1 and as 0, otherwise. The endpoint will utilize imputed values per Section 7.7.

• Analysis of the Endpoint

For each frequency, the incidence of shifts from no signal at baseline to any signal at each post-baseline visit for treated ears will be summarized using frequencies and percentages by visit and treatment group for subjects with no signal at baseline in the FAS.

7.7.7. Shift from baseline of no signal to any signal in two contiguous frequencies

• Computation of the Endpoint

Shifts from no signal in two contiguous frequencies at baseline to any signal in two contiguous frequencies at each post-baseline visit will be computed in subjects in the FAS with no signal (missing/imputed hearing response) at baseline in the treated ear for any two contiguous frequencies. At each post-baseline visit, subjects with any signal (any non-missing/not imputed hearing response) in the treated ear at the same two contiguous frequencies will be flagged as 1 and as 0, otherwise. The endpoint will utilize imputed values per Section 7.7.

• Analysis of the Endpoint

The incidence of shifts from no signal in two contiguous frequencies at baseline to any signal in two contiguous frequencies at each post-baseline visit for treated ears will be summarized using frequencies and percentages by visit and treatment group for subjects in the FAS with no signal in any two contiguous frequencies at baseline in the treated ear.

7.7.8. Shift from baseline of no signal to any signal in three contiguous frequencies

• Computation of the Endpoint

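### The 9-16 kHz mean averages no-response values as if they were measured thresholds, so it understates change in ears well beyond the audiometer limit; the improvement rule beside it is also printed with the wrong sign

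*SAP*

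**What the plan says.** SAP 7.7 deals with "no response due to a subject's audiometric threshold greater than the maximum calibrated dB of the equipment at a given frequency". After Screening, such a value "will be imputed using the maximum dB for the audiometry equipment plus 5 dB" and is classed as no signal. A no response at Screening stays missing.

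The value is then used in several places:

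- **7.7.2:** "the mean dB HL threshold will be derived by averaging the AC audiometry dB HL thresholds over 9-16 kHz frequencies", with missing values imputed under 7.7. The result is summarised by visit and arm.
- **7.7.3 and 7.7.4:** the criteria of at least 10, 15 or 20 dB carry the sentence "The endpoint will utilize imputed values per Section 7.7". Improvement is scored 1 "if the post-baseline threshold – baseline threshold is ≥10 dB HL for two contiguous frequencies", with parallel wording for any single frequency.
- **7.7.5:** composites are built from those criteria. An optional GEE model uses "baseline mean dB HL threshold (AC over 9-16 kHz), interaction between baseline mean dB HL threshold (AC over 9-16 kHz) and visit" among its terms.
- **7.7.6 to 7.7.8:** shifts from no signal to any signal are reported separately. At each frequency the group is "subjects in the FAS with no signal (missing/imputed hearing response) at baseline in the treated ear".

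Protocol section 9 lists extended high frequency audiometry as a secondary endpoint. It is not in the fixed sequence of SAP 7.1.4.

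**The concern.** A no response says only that the threshold lies above what the audiometer can deliver. Once it is replaced by the limit plus 5 dB and averaged, the mean treats a bound as a measurement. An ear far beyond the limit can gain hearing without its recorded value moving, or with the value moving by less than the true gain. The visit means in 7.7.2 would then show a muted change in both arms, and a real difference between arms would be muted as well.

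The SAP expects such ears, since 7.7.6 to 7.7.8 are written for them. Yet 7.7.2 gives no count of imputed frequencies and no companion summary without them. A reader of the table could not tell a true absence of change from censoring.

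**Working it through.** The plan states no figure for this endpoint, so there is none to reproduce. The check applies the scoring rule directly.

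**Inputs from the SAP.** A no response is recorded as L + 5, where L is the audiometer limit (7.7). The mean covers six frequencies: 9, 10, 11.2, 12.4, 14 and 16 kHz. Under section 3, efficacy baselines average Lead-in and Day 1. Both visits fall after Screening, so both are imputed when there is no response.

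**Assumed, because not given.** The value of L, the distance x of the true baseline threshold beyond L, 5 dB test steps, and the share of no responses. A gain means a fall in threshold.

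**1. One frequency.** The true baseline is L + x, the recorded baseline is L + 5 and the true gain is g.

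- If the ear now responds, the recorded gain is (L + 5) - (L + x - g) = g - (x - 5).
- If it still does not respond, the recorded gain is 0.

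The shortfall x - 5 is positive only when x exceeds 5. At x = 5, one test step beyond the limit, nothing is lost. With g = 10, the recorded gain is 10 at x = 5, 5 at x = 10 and 0 at x = 15.

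**2. The six-frequency mean.** Suppose every frequency truly gains 10 dB and k of the six start at L + 15. The recorded mean gain is 10 x (6 - k)/6: 8.3 dB for k = 1, 5.0 dB for k = 3 and 0 dB for k = 6.

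**3. A spread of ears.** This simulation used six frequencies with a limit of 80 dB, true thresholds with SD 20 dB, correlation 0.8 between frequencies, an 8 dB rise from each frequency to the next, 4 dB visit noise, 5 dB steps, a two-visit baseline and a true 10 dB gain everywhere.

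| Share with no response at both baseline visits | Mean gain, 7.7.2 rule | Mean gain, frequencies measured at baseline |
|---|---|---|
| 25% | 8.2 dB | 9.8 dB |
| 91% | 1.3 dB | 9.1 dB |

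With 56 ears per arm (112/2), the between-arm z for the second mean was higher than for the first in every scenario, even though ears with nothing measurable drop out of it.

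**4. The responder criteria.** For criterion c, the recorded follow-up value must be at most L + 5 - c, so the true gain needed is c + (x - 5). For c = 10 this is 6, 8, 10, 15, 20 and 30 dB at x = 1, 3, 5, 10, 15 and 25.

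**5. The printed sign.** 7.7.3 and 7.7.4 subtract baseline from follow-up and require a positive result of at least c. A higher dB threshold is worse hearing, so this counts worsening. Read literally, an ear with no response at baseline can reach at most (L + 5) - (L + 5) = 0 when the limit is unchanged, and so can never qualify.

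**The case against.** The rule has a sound rationale. On a 5 dB grid, L + 5 is the lowest value consistent with no response, so a gain counted from it is at least as large as stated. Both blinded arms are treated alike. The effect is dilution, not a manufactured difference. Sections 7.7.6 to 7.7.8 already report newly audible frequencies with no dB criterion, and 7.7.1 summarises each frequency. Unlike 7.6.6 for the pure tone average, 7.7 defines no mean-change endpoint. All of this stands and keeps the point small. It does not repair the 7.7.2 table, whose visit means will be compared with one another and which does not show how much of each mean is imputed.

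Three stronger readings are tempting and are not supported:

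- **Every ear beyond the limit must gain more than the criterion.** Step 4 shows this only for x above 5. At x = 5 the requirement is exact, and closer in it is lower.
- **Site equipment distorts the results.** The arithmetic allows it: an ear going from 95 to 80 dB scores 0 with a limit of 70 or 75, 5 at 80, 10 at 85 and 15 at 90 or above. But the documents say only that center frequencies vary slightly. They do not show that limits differ between sites or between one ear's visits.
- **The responder criteria should be confined to frequencies measured at baseline.** In the same simulation of the first 7.7.5 composite, that dropped 3% to 77% of ears and lowered the between-arm z in every scenario, for example from 11.4 to 9.6 and from 6.3 to 5.4. An ear silent at the top frequencies can still qualify at lower ones, and the restriction discards certain large gains.

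**Conclusion.** The point holds for the mean in 7.7.2. It averages right-censored values with measured ones and understates change wherever the true threshold is more than 5 dB beyond the limit. With a true 10 dB gain the recorded mean gain is about 8.2 dB at a 25% no-response share and about 1.3 dB at 91%. Those figures rest on the assumed limit, spread, correlation and noise in step 3. The actual share and limits are not in the documents, so the loss in this trial cannot be stated.

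The same censored mean is the baseline covariate in the optional 7.7.5 GEE. The responder definitions are conservative for ears far beyond the limit, but they are acceptable as the main rule. The reversed sign in 7.7.3 and 7.7.4 is a plain text error and needs no assumption.

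A reader might infer that the trial's efficacy conclusion is at risk. It is not: the primary analysis, the fixed testing sequence and the sample size do not use these endpoints.

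**What to change.** - **7.7.2:** keep the planned mean. Beside it, report by visit and arm the mean threshold and its change from baseline over the frequencies with a measured response at that ear's baseline visits. Add the number of imputed frequencies per ear, by arm and visit. The selection uses only pre-treatment data.
- **Baseline:** state which baseline applies. Section 3 averages Lead-in and Day 1 for efficacy endpoints and takes the last value for other analyses. Table 7-2 does not mark this block as efficacy, while Protocol 13.1.4 lists it among the efficacy measurements.
- **7.7.3 and 7.7.4:** write improvement as baseline minus follow-up at or above the criterion. Sections 7.6.3 and 7.6.4 print the same reversed sign and need the same correction. Otherwise leave the definitions in 7.7.3 to 7.7.5 as they are.

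The cost is SAP wording, a little programming and one extra descriptive table. The no-signal classification it needs is already in 7.7. The drawback is that ears with no measurable frequency at baseline do not contribute to the added mean. For those ears, 7.7.6 to 7.7.8 remain the informative summaries.
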